1 **Background:** Glioma imaging, used for diagnostics, treatment planning and follow-up, is
2 currently based on standard magnetic resonance imaging (MRI) modalities (T1 contrast-
3 enhancement for gadolinium-enhancing gliomas and T2/ Fluid attenuated inversion
4 recovery (FLAIR) hyperintensity for non-enhancing gliomas). The diagnostic accuracy of
5 these techniques for the delineation of gliomas is suboptimal.

6 **Objective:** To assess the diagnostic accuracy of advanced neuroimaging compared with
7 standard MRI modalities for the detection of diffuse glioma infiltration within the brain.

8 **Methods:** A monocenter, prospective, diagnostic observational study in adult patients
9 with a newly diagnosed, diffuse infiltrative glioma undergoing resective glioma surgery.
10 Forty patients will be recruited in three years. Advanced neuroimaging will be added to
11 the standard preoperative MRI. Serial neuronavigated biopsies in and around the glioma
12 boundaries, obtained immediately preceding resective surgery, will provide
13 histopathologic and molecular characteristics of the regions of interest, enabling
14 comparison with quantitative measurements in the imaging modalities at the same
15 biopsy sites.

16 **Expected outcome:** We hypothesize that a combination of positron emission
17 tomography, MR spectroscopy and standard MRI will have a superior accuracy for
18 glioma delineation compared to standard MRI alone. In addition, we anticipate that
19 advanced imaging will correlate with the histopathologic and molecular characteristics
20 of glioma.

21 **Discussion:** In this clinical study, we determine the diagnostic accuracy of advanced
22 imaging in addition to standard MRI to delineate glioma. The results of our study can be
23 valuable for the development of an improved standard imaging protocol for glioma
24 treatment.

25

26 **General information**

27 The study is titled: 'Frontiers in advanced imaging of unexplored glioma regions
28 (FRONTIER study)' (www.trialregister.nl, unique identifier NTR5354). Overall study
29 dates are September 2014 to September 2017. Funding agencies: Cancer Center
30 Amsterdam and the Dutch Cancer Society.

31 Investigation site: VU University Medical Center (VUmc), [name]
32 Amsterdam, The Netherlands.

33 Principle investigator: [name], PhD, Department of Neurosurgery.

34 Investigators: [name], MD, PhD, and [name], MD, Department of
35 Neurosurgery; [name], MD, PhD, Department of Neurology; [name], MD,
36 PhD, Department of Pathology; [name], PhD, Department of Physics & Medical
37 Technology; [name], MD, PhD, [name], MSc, PhD and [name], MD, PhD,
38 Department of Nuclear Medicine & PET Research.

39

40 **Rationale and background information**

41 Gliomas represent 80-90% of parenchymal brain tumors in adults with an incidence of
42 5.9 per 100.000 person-years: approximately 1000 patients per year in The
43 Netherlands. ¹ Most gliomas show extensive infiltration in the brain parenchyma. These
44 so-called diffuse gliomas universally recur, without exception resulting in death despite
45 standard treatment, which consists of as extensive as possible resection, followed by
46 radiation and chemotherapy.

47 Both resective surgery and adjuvant radiation therapy are based on T1 contrast-
48 enhancement for gadolinium-enhancing gliomas and on T2/ Fluid attenuated inversion
49 recovery (FLAIR) hyperintensity volume outlines for non-enhancing gliomas. This
50 strategy is founded on early and preliminary observations, and has remained unchanged
51 since. ^{2,3} Diffuse gliomas recur locally in the vast majority of patients, even after
52 seemingly radical surgical removal and radiation therapy with 2 cm margins. This, and
53 the fact that glioma infiltration has been demonstrated to extend up to two centimeters
54 beyond standard MRI outlines, underscores that up till now delineation of these
55 neoplasms has been less than optimal. ⁴⁻⁷

56 Several publications provide arguments for underestimation of the spread of diffuse
57 gliomas using standard MRI and potential benefit from advanced MRI and positron
58 emission tomography (PET) imaging. Advanced imaging, such as diffusion-weighted
59 imaging (DWI), perfusion-weighted imaging (PWI), magnetic resonance spectroscopy
60 (MRS) and PET, has been shown to be able to identify tumor in areas of normal standard
61 MRI signal. ⁸⁻¹⁰

62 Our study addresses a clinically relevant research question, which so far has not been
63 adequately answered: What is the best neuroimaging approach to discriminate areas
64 with glioma infiltration from brain tissue without glioma cells?

65

66 **Study Goals and Objectives**

67 The goal of this study is thus to determine the best neuroimaging approach for glioma
68 delineation.

69 The specific objectives are:

- 70 - To assess the increase in diagnostic accuracy of adding advanced neuroimaging
71 modalities to standard MRI for the detection of diffuse glioma infiltration within
72 the brain
- 73 - To correlate the information obtained by standard and advanced imaging to
74 histologic and molecular characteristics of the tissue.

75 We hypothesize that advanced neuroimaging, in combination with standard MRI, will
76 have a superior diagnostic accuracy in comparison with standard MRI alone. Besides, we
77 hypothesize that histological and molecular characteristics of (different areas of) glioma
78 will correlate better with advanced imaging than with standard imaging.

79

80 **Study Design**

81 The study design is a monocenter, prospective, diagnostic observational study.

82

83 **Methodology**

84 Subjects

85 *Inclusion criteria*

86 Patients of 18 years and older with a MRI interpretation of a diffuse glioma by an
87 experienced neuroradiologist, and who have an indication for resective surgery; the
88 indication confirmed by the multidisciplinary neuro-oncology tumor board.

89

90 *Exclusion criteria*

91 Patients who are pregnant or have undergone previous brain surgery, cranial irradiation
92 or chemotherapy. Patients with other brain pathology on MRI, such as stroke or multiple
93 sclerosis. Patients with a tumor located infratentorially or in the spinal cord.

94

95 *Withdrawal criteria*

96 Patients who do not successfully undergo one PET scan. A summary of all criteria is
97 given in table 1.

98

99 Study description

100 The study is separated into two phases (Figure 1). In both phases, standard and
101 advanced imaging will be performed pre-operatively (Table 2). Immediately preceding
102 resective surgery, serial image-guided neuronavigated biopsies in and around the
103 glioma boundaries will be obtained using a stereotactic drilling technique.¹¹ Two
104 samples are collected from each biopsy location, one for assessment of histopathologic
105 characteristics and one for molecular analysis.

106 Phase I is designed to decide on the optimal PET tracer, to simplify PET scanning
107 methodology and to develop a robust MRI protocol for glioma volume estimation. Eight
108 patients will receive a dynamic PET protocol with invasive blood sampling, and image-
109 derived carotid input function for metabolite analysis of
110 [18F-]Fluoroethyl-tyrosine (FET) and [11C-]Choline (CHO) tracers, as well as advanced
111 MR imaging. The data obtained will be used to establish a simplified PET protocol and to
112 determine which of both PET tracers will be further pursued in the next study phase.
113 To obtain a total sample size of 20 patients with a high-grade glioma (WHO grade III or
114 IV) and 20 with a low-grade glioma (WHO grade II), 20 additional patients will receive
115 single advanced MRI and selected simplified PET imaging in the second phase to
116 complete the data acquisition according to the sample size calculation for the main
117 research question.

118

119 Outcome measures

120 *MRI*

121 MRI will be performed using the Philips Achieva whole-body 3.0T MR-scanner, equipped
122 with the standard head coil. Table 2 shows the different techniques.

123

124 *PET*

125 PET will be performed using the Philips Gemini time-of-flight (TOF) PET-CT scanner or
126 the Philips Ingenuity TOF PET/MRI-scanner. After intravenous administration of 370
127 megabecquerel (MBq) of [¹⁵O]H₂O a 10 min dynamic scan is acquired. This is followed
128 by a 40 min dynamic scan after injection of 200 MBq CHO. With a minimum of 4 hours
129 after injection of CHO the FET scan will be performed the same day using 200 MBq FET
130 and a scan time of 90 minutes. During the scans manual blood samples are withdrawn in
131 order to calibrate the online collected arterial input functions and to derive a fully

132 metabolite-corrected plasma input function.

133

134 Of each biopsy site qualitative (high, normal or low signal) and quantitative parameters
135 will be acquired by an experienced neuroradiologist and a nuclear medicine physician
136 (Table 2).

137

138 *Pathology*

139 Of each biopsy location one sample will be processed for histopathologic analysis and
140 the other sample for molecular analysis. Histopathologic analysis will be performed
141 using hematoxylin-and-eosin (H&E) staining and immunohistochemical markers to
142 assess cellularity, glioma infiltration, proliferation, microvascular changes, and necrosis.
143 Molecular analysis will include assessment of DNA mutations, deletions, amplifications
144 and RNA expression profiling. Two experienced neuropathologists will evaluate
145 independently, and blinded for the imaging results, all biopsies and designate those as:
146 normal brain tissue; diffuse glioma with few, moderate or many tumor cells in a
147 background of pre-existent brain tissue; highly cellular glioma without (apparent)
148 preexistent brain tissue remaining; uninformative.

149

150 **Discussion**

151 Few studies investigate the diagnostic accuracy of glioma delineation, and most of these
152 studies assess only one or two imaging modalities. This can at least partly be explained
153 by the logistic challenge of multimodality preoperative imaging and of obtaining
154 multiple image-guided biopsies. Nevertheless, studies that provide a direct comparison
155 of multiple imaging modalities with histopathologic data are necessary to determine the
156 optimal imaging modality for the delineation of diffuse gliomas. Using combined PET-
157 MRI will help to reduce the number of scans necessary for multimodality imaging, while
158 frameless stereotactic techniques will facilitate the acquisition of multiple image-guided
159 biopsies with good accuracy within a limited time.

160

161 The importance of adequate glioma delineation is underscored by reports describing
162 that (near) radiologically complete resection of MRI abnormalities (T1-weighted
163 gadolinium-enhanced MRI for HGG and on T2/FLAIR-weighted MRI for LGG) is
164 correlated with improved survival.¹²⁻¹⁷ A resection based on modalities with superior

165 delineation could result in even more complete resection and thus holds promise for
166 even longer survival, and conversely to identify patients with glioma infiltration beyond
167 meaningful surgical therapy, so that useless, and possibly harmful, resections can be
168 avoided. Moreover, evidence accumulates that subsequent therapeutic modalities are
169 more successful after resection that is as complete as possible. ¹⁶

170

171 **Trial status**

172 Patient recruitment was initiated on September 1, 2014.

173

174 **Safety Considerations**

175 Because neuronavigated biopsy has a risk of less than 2% of intracranial hemorrhage
176 with consequences for the patient, the number of biopsy trajectories is limited to three.

177 ^{18,19} Since the biopsy procedure is immediately followed by a craniotomy for tumor
178 resection, possible hemorrhages can be directly identified and removed. The tumor
179 resection will be performed according to standard care.

180 All adverse events reported spontaneously by the subject or observed by the investiga-
181 tor or his staff will be recorded in the protocol case report forms (CRF) using the
182 Common Terminology Criteria for Adverse Events classification. ²⁰ All serious adverse
183 events (SAEs) will be reported through the web portal ToetsingOnline
184 (<https://www.toetsingonline.nl>) to the accredited Medical Ethical Committee (METC)
185 that approved the protocol. SAEs that result in death or are life threatening are reported
186 expeditiously.

187

188 **Follow-up**

189 All patients will receive standard follow-up, which consists of postoperative clinical
190 admission for as long as needed and an outpatient appointment eight weeks after the
191 procedure. Apart from that, postoperative adjuvant chemo- and/or radiotherapy will be
192 installed according to histopathologic and molecular classification of the tumor, as
193 discussed postoperatively at the neuro-oncology tumor board meetings. All adverse
194 events will be followed until they have abated, or until a stable situation has been
195 reached.

196

197 **Data Management and Statistical Analysis**

198 Data will be collected on electronic CRF (eCRF). The eCRF is only assessable by the

199 principal and the study investigator. The eCRF will be completed on site by an
200 investigator. The principal investigator will review the collected data.
201 The number of biopsies and patients required to compare the area under the curve
202 (AUC) of the receiver operating characteristic (ROC) curves depend on the reference
203 AUC (t1), the minimal relevant AUC from the improved imaging (t2), the ratio of non-
204 tumor and tumor biopsies (ratio), the correlation of imaging within patients (r), the
205 average number of biopsies per patient (s), the correlation of histopathologic
206 quantification between biopsies within patients (rho), the type I error (alpha) and the
207 type II error (beta) ²¹⁻²³. Under the assumptions of t1 0.6, t2 0.8, ratio 0.25, r 0.5, s 6, rho
208 0.2, alpha 0.05 and beta 0.2, 20 patients per glioma target volume subgroup are
209 required. The overall study population then comprises 20 non-enhancing and 20
210 enhancing glioma patients, each stratum providing at least 120 biopsies. For testing the
211 correlation between simplified and full quantitative measurement of input function in
212 dynamic PET scanning a sample size of eight is mostly used in pilot studies. Due to the
213 experience with other trials we will include this number in phase I. In phase II 32
214 patients will be included to obtain the total of 40 patients from our sample size
215 calculation.
216 Continuous variables will be described as a mean with standard deviation if the
217 distribution is symmetric and as a median with minimum and maximum if it is skewed.
218 Categorical variables are presented as numbers with percentages. Data analysis will be
219 performed using R. AUCs are compared using a nonparametric resampling test using
220 pROC in R. ²⁴⁻²⁶ Next, multivariate logistic regression analysis modeling histopathology
221 by quantitative imaging is performed using Bayesian models.

222

223 **Quality Assurance**

224 As the METC of VU University Medical Center (VUmc) decided it was unnecessary to
225 appoint a Data Safety Monitoring Board for this study, the progress of this study will be
226 monitored by the Clinical Research Bureau of VUmc.

227

228 **Expected Outcomes of the Study**

229 We expect that advanced imaging in combination with standard imaging, will have a
230 superior diagnostic accuracy for glioma delineation compared with current standard
231 imaging. This delineation could help neurosurgeons, neurologists, radiation oncologists

232 and medical oncologists in their clinical decision-making. Next, studies comparing
233 glioma resection or radiotherapy using standard versus standard plus advanced imaging
234 can be conducted to investigate possible influences on clinical outcome.
235 The expected correlation between advanced imaging and histologic and molecular
236 characteristics could provide biomarkers for prognosis and choice of therapy, as well as
237 further insight into glioma imaging

238

239 **Duration of the Project**

240 We anticipate that phase I will take 12 months and phase II 24 months, aiming for a total
241 study duration of three years.

242

243 **Project Management**

244 The principal investigator, [name], will lead the study. [name] will be
245 responsible for the MRS data, [name] for the MRI data, [name] and Dr.
246 [name] for the PET data, and [name] for the pathology data. The study
247 investigator, [name], MSc, will coordinate the logistics and of the study as well as
248 the interpretation of the results.

249

250 **Ethics**

251 The study is approved by the METC of VUmc and will be conducted according to the
252 principles of the Declaration of Helsinki and in accordance with the Medical Research
253 Involving Human Subjects Act. Explicit written consent will be obtained from all patients
254 in this study.

255 **Disclosures**

256 Financial support was provided by grant CCA2012-2-05 of the Cancer Center

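### The two groups of 20 are set by WHO grade in the study description but by MRI enhancement in the sample size calculation, so 20 per powered stratum is not guaranteed

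*Protocol*

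**What the plan says.** **Protocol, Methodology, Study description.** The composition of the sample is given by histology: "To obtain a total sample size of 20 patients with a high-grade glioma (WHO grade III or" followed by "IV) and 20 with a low-grade glioma (WHO grade II), 20 additional patients will receive" imaging in phase II. The stated purpose is to "complete the data acquisition according to the sample size calculation for the main" research question, so the grade split is presented as the result of the sample size calculation. (The phase II count in that sentence also differs from the one in the statistics section. That is a separate matter and is not pursued here.)

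**Protocol, Data Management and Statistical Analysis.** The calculation itself asks for 20 patients per glioma target volume subgroup and then says: "The overall study population then comprises 20 non-enhancing and 20" "enhancing glioma patients, each stratum providing at least 120 biopsies. For testing the" The inputs begin: "Under the assumptions of t1 0.6, t2 0.8, ratio 0.25, r 0.5, s 6, rho" 0.2, with alpha 0.05 and beta 0.2.

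**Elsewhere.** The abstract and the Rationale tie T1 contrast to enhancing gliomas and T2/FLAIR to non-enhancing ones. The Discussion attaches the same two sequences to grade: "gadolinium-enhanced MRI for HGG and on T2/FLAIR-weighted MRI for LGG) is" linked to survival. The inclusion and exclusion criteria mention neither grade nor enhancement.

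**The concern.** Both sections describe the same 20 + 20 = 40 patients and appeal to one calculation, but they sort the patients by different variables. Grade is a tissue result. Patients enter on an MRI interpretation, previous brain surgery is an exclusion, and biopsies are taken immediately before resection, so grade is not in hand when a patient is enrolled. Enhancement can be read on the MRI before surgery.

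The requirement of 20 patients and at least 120 biopsies applies to each stratum separately. If the team works to the grade split, the numbers of enhancing and non-enhancing patients are left to chance, and one of the two powered comparisons may have fewer patients than the calculation asks for. A reader of the final report would also be unable to tell which partition was the planned one.

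**Working it through.** **1. The two definitions side by side**

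| | Study description | Data Management and Statistical Analysis |
|---|---|---|
| Group 1 | 20 with WHO grade III or IV | 20 enhancing |
| Group 2 | 20 with WHO grade II | 20 non-enhancing |
| Source of the label | tissue | preoperative MRI |
| Basis cited | the sample size calculation | is the sample size calculation |

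Nothing in the protocol equates the rows, gives a concordance figure or says which label controls recruitment.

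**2. Reproducing the stated 20 per group**

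Inputs from the protocol: t1 = 0.6, t2 = 0.8, ratio of non-tumour to tumour biopsies k = 0.25, r = 0.5, s = 6, rho = 0.2, alpha = 0.05, beta = 0.2. Assumed, because not stated: the Obuchowski binormal variance, a one-sided test, and the design effect 1 + (s − 1) × rho = 1 + 5 × 0.2 = 2.0.

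- V = 0.0099 × exp(−A²/2) × [(5A² + 8) + (A² + 8)/k], with A = 1.414 × z(AUC)
- A1 = 0.358 gives V1 = 0.382; A2 = 1.190 gives V2 = 0.257
- VA = V1 + V2 − 2r√(V1·V2) = 0.326
- Tumour biopsies = (1.645 + 0.842)² × 0.326 / 0.2² = 50.4
- All biopsies = 50.4 × 1.25 = 63.0; with the design effect, 125.9
- Patients = 125.9 / 6 = 21.0, against the stated 20

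Other choices move this figure. With the same variance formula, the null variance gives 23.3 one-sided; two-sided gives 26.6 or, with the null variance, 29.8. A two-sided test with a non-standard design effect of 1.5 gives 20.0. The protocol does not say which was used. Its 120 biopsies per stratum agree with 20 × 6.

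**3. What a 20/20 grade split gives by enhancement**

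Let a be the share of high-grade tumours that do not enhance and b the share of low-grade tumours that do. The protocol gives neither.

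- Enhancing = 20(1 − a) + 20b; non-enhancing = 20a + 20(1 − b)
- If a = b, the counts stay 20/20, although the patients in each stratum differ. Only the net mismatch changes stratum size.

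Assumed range: a from 0.10 to 0.40, b from 0 to 0.20.

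| a | b | Enhancing | Non-enhancing | Smaller stratum |
|---|---|---|---|---|
| 0.10 | 0.20 | 22 | 18 | 18 |
| 0.25 | 0.10 | 17 | 23 | 17 |
| 0.40 | 0 | 12 | 28 | 12 |

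**4. Power in the smaller stratum, same variant as step 2**

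With N patients, the effective number of tumour biopsies is m = 6N / (2.0 × 1.25), and power = Φ(0.2 × √(m/VA) − 1.645).

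| N | Biopsies | m | Power |
|---|---|---|---|
| 20 | 120 | 48.0 | 78.3% |
| 18 | 108 | 43.2 | 74.5% |
| 17 | 102 | 40.8 | 72.3% |
| 12 | 72 | 28.8 | 59.3% |

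**5. Sensitivity to the method**

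A two-sided test with everything else unchanged gives 68% at N = 20 and 47% at N = 12. With s = 6 and k = 0.25, a patient contributes on average 4.8 tumour and 1.2 non-tumour biopsies. Class-specific design effects are then 1 + 3.8 × 0.2 = 1.76 and 1 + 0.2 × 0.2 = 1.04. Across Obuchowski and Hanley-McNeil variances, one- and two-sided, these give 81-93% at N = 20, 74-89% at N = 17 and 58-78% at N = 12. The level of power depends on the method. In each variant it falls as the smaller stratum shrinks.

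**The case against.** The strongest reply is that there is only one design here and the grade labels are shorthand. The study description defers to the sample size calculation, that calculation speaks of target volume subgroups and enhancement, and the Discussion uses high and low grade for the same T1/T2-FLAIR split. This is a fair reading and it indicates which label should govern. It does not remove the conflict, because the study description defines its groups explicitly by WHO grade and no sentence makes the labels equivalent.

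Three stronger readings are tempting, and the documents do not carry them:

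- **That the trial will recruit to a grade quota or analyse by grade.** No section sets an enrolment rule or an analysis by grade. The shortfall in the working is conditional on the grade split being the one followed.
- **That each stratum has its own standard-MRI comparator, so grade groups would mix comparators.** The abstract and the Rationale describe current practice in those terms, and the term target volume subgroup suggests the link. The objective, however, compares against standard MRI as a whole, and the AUC paragraph names no stratum-specific comparator. It is an inference.
- **That power drops by a known amount.** The discordance shares are assumptions, the 12-patient case is one extreme of the assumed range, and at the midpoint some variants keep power above 80%.

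It also stands that the total of 40 and the requirement of 20 per stratum are unaffected.

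**Conclusion.** The protocol contradicts itself on the composition of its sample. The same two groups of 20 are defined by a tissue result in one section and by an MRI feature in another, and filling 20/20 on the first does not guarantee 20 on the second. This needs no assumption beyond the text.

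The size is conditional. Under the assumed discordance, the smaller powered stratum has between 12 patients (one extreme) and 20 (no net mismatch), with 17 at the midpoint. In the variant used in the working, power falls from about 78% to 72% at the midpoint and to 59% at the extreme. Those figures rest on assumed discordance shares and on a variance formula, design effect and sidedness that the protocol leaves unstated. They show that the calculation has little slack under that variant; they do not predict the loss in this trial.

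**What to change.** In the study description, replace the grade-based groups with 20 enhancing and 20 non-enhancing gliomas as seen on the inclusion MRI, matching the statistics section. State that recruitment to 20 per stratum and the powered AUC comparison both use this one stratifier. WHO grade can still be reported descriptively. If the text is to say that each stratum has its own standard-MRI comparator, it should state this expressly, because at present it can only be inferred.

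The cost is protocol wording. Enhancement is visible before surgery and the planned total of 40 does not change.

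### Phase II is given as 20 patients in the study description and 32 in the statistics section; only 32 reaches the stated total of 40

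*Protocol*

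**What the plan says.** Three places in the protocol bear on the size of phase II.

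- **Methodology, Study description.** Phase I has eight patients: "methodology and to develop a robust MRI protocol for glioma volume estimation. Eight" patients undergo the dynamic PET protocol. The next paragraph sets the goal, "To obtain a total sample size of 20 patients with a high-grade glioma (WHO grade III or" (the sentence runs on) "IV) and 20 with a low-grade glioma (WHO grade II), 20 additional patients will receive" the phase II imaging. The sentence ends by saying that this completes data acquisition as the sample size calculation requires.
- **Data Management and Statistical Analysis.** The calculation uses "t1 0.6, t2 0.8, ratio 0.25, r 0.5, s 6, rho" (continuing) "0.2, alpha 0.05 and beta 0.2, 20 patients per glioma target volume subgroup are" required. This makes 40 patients, with at least 120 biopsies in each stratum. On the phases, it keeps eight for the pilot question and continues: "experience with other trials we will include this number in phase I. In phase II 32" "patients will be included to obtain the total of 40 patients from our sample size" calculation.
- **Abstract, Methods.** "Forty patients will be recruited in three years".

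**The concern.** Both sections describe the same phase and say that its patients complete the same sample size calculation, yet they give different numbers. The figure in the study description also fails within its own sentence, because eight plus 20 is not 20 plus 20.

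The study description is a natural place to look when planning recruitment, scanner time and tracer supply. If phase II were run to 20 patients, the AUC comparison in each subgroup would rest on fewer patients and biopsies than the sample size section requires.

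**Working it through.** **Head count**

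- Study description: 8 + 20 = 28, which is 40 − 28 = 12 short (12/40 = 30%).
- Statistics section: 8 + 32 = 40, which agrees with 20 + 20 and with the abstract.
- Reading the 20 as 20 per group does not help: 8 + 40 = 48.

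**Patients and biopsies per stratum if phase II had 20**

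With an even split (an assumption), 28/2 = 14 patients per stratum and 14 × 6 = 84 biopsies. The plan requires 20 patients and 20 × 6 = 120 biopsies.

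**Reproducing the stated 20 per subgroup**

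Inputs from the statistics section: AUCs 0.6 and 0.8, non-tumor to tumor ratio R = 0.25, r = 0.5, s = 6 biopsies per patient, rho = 0.2, alpha 0.05, beta 0.2. The protocol gives no formula and no sidedness. The assumptions here are the Obuchowski binormal variance, r taken as the correlation of the two AUC estimates, one-sided alpha, and one common design effect.

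- V(A) = 0.0099 · exp(−a²/2) · [(5a² + 8) + (a² + 8)/R], with a = 1.414 · z(A).
- A = 0.6: a = 0.358, V1 = 0.382. A = 0.8: a = 1.190, V2 = 0.257.
- Variance of the difference: VA = V1 + V2 − 2r√(V1·V2) = 0.382 + 0.257 − 0.314 = 0.326 (from unrounded values).
- Tumor biopsies: (1.645 + 0.842)² × 0.326 / 0.2² = 50.4.
- All biopsies: 50.4 × 1.25 = 63.0.
- Design effect: 1 + (6 − 1) × 0.2 = 2, so 125.9 biopsies (from unrounded values), and 125.9/6 = 21.0 patients.

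The Hanley-McNeil variance in the same setting gives 18.5 patients. The stated 20 lies between the two. With R = 0.25 and the common design effect, two-sided variants give 23.5 to 29.8, so one-sided alpha is the closer match.

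**Power at 20 and at 14 patients per stratum**

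Effective tumor biopsies are patients × 6 / 2 / 1.25, that is 48 at 20 patients and 33.6 at 14. Power is Φ(0.2·√n/√VA − 1.645), with √VA = 0.571.

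- 20 patients: 0.2 × √48 / 0.571 − 1.645 = 0.78, power 78%.
- 14 patients: 0.2 × √33.6 / 0.571 − 1.645 = 0.39, power 65%.

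**Sensitivity to what the protocol leaves open**

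Each row gives the range over the Obuchowski and Hanley-McNeil variances, with and without a separate null variance, at R = 0.25. Class-specific design effects use 4.8 tumor and 1.2 non-tumor biopsies per patient: 1 + 3.8 × 0.2 = 1.76 and 1 + 0.2 × 0.2 = 1.04.

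| Design effect | Alpha | Power at 20 | Power at 14 |
|---|---|---|---|
| Common, 2.0 | one-sided | 74–83% | 60–70% |
| Common, 2.0 | two-sided | 62–73% | 46–58% |
| Class-specific | one-sided | 91–95% | 80–87% |
| Class-specific | two-sided | 84–91% | 69–78% |

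Across these sixteen combinations the loss runs from 8.4 to 16.5 percentage points; fourteen of them lie between 9.7 and 15.6.

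**The case against.** The strongest reply is that the protocol resolves the slip itself. The study description's own sentence names 20 + 20 as its goal, the statistics section gives 8 + 32 = 40, and the abstract says forty. No passage states 28. The 20 looks like a drafting error for 32, and the power loss arises only if someone follows that one number against everything around it.

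This stands as far as it goes. A reader might infer that the trial as written ends at 28 patients and forfeits its power, and the document does not support that. It sets no stop at 28, and whether power falls below 80% depends on unstated choices: with class-specific design effects and one-sided alpha, 14 per stratum still gives 80–87%. That setting gives 91–95% at 20 patients, however, so it does not reproduce the plan's own requirement of 20.

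The figure of 14 per stratum also needs care. It assumes an even split, and the two sections define the groups of 20 differently (WHO grade in one, enhancement in the other). That is a separate matter.

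The reply does not remove the contradiction. Both numbers stand in running text as the size of the same phase, no further cohort is described that would bridge the gap, and this is a misstated figure rather than a detail left to an analysis plan.

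**Conclusion.** The phase II size in the study description is wrong as written. With eight patients in phase I, 32 is the only phase II number that reaches the stated 40. This follows from the head count alone and needs no statistical assumption.

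The consequence is conditional on the figure being followed: 12 patients (30%) short, with roughly 10 to 16 points of power lost per stratum. The fall from about 78% to 65% is one illustration, chosen because its setting comes close to the plan's own 20 per subgroup. It rests on an even split, one-sided alpha, a common design effect of 2 and the Obuchowski variance.

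**What to change.** In Methodology, Study description, change the 20 additional patients in phase II to 32, so that the sentence agrees with its own 20 + 20, with the statistics section and with the abstract. Check that Figure 1, which was not available for this review, carries the same number.

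The cost is a one-number correction. The total of 40, the sample size calculation and the analysis are unchanged.
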